18. SCHEDULE AND PROPOSED END DATE

The selection and inclusion period for patients to participate in the study is set between June 2019 and August 2019.

The planned date for the commencement of the trial and the treatment is the end of June and July 2019. The planned date for the completion of the exercise program in both groups is predicted to be at the end of August 2019.

19. INTERVIEWS, QUESTIONNAIRES OR INSTRUMENTS TO BE USED IN THE TRIAL

The IELT measurements will be collected by self-registration after each week of treatment (APPENDIX I).

In order to collect the information regarding the perception of ejaculation, the Premature Ejaculation Profile (PEP) will be used (Patrick et al., 2009), a self-reported instrument consisting of four measurements (perceived control over ejaculation, personal stress related to ejaculation, satisfaction with sexual relationships, and interpersonal difficulty related to ejaculation). These will give an overall profile and score (Patrick et al., 2009), where the lowest scores express the lowest performance. The reliability coefficient between ranges from 0.66 to 0.83 and its validity was contrasted with dapoxetine and Intravaginal Ejaculation Latency Times (IELT). This instrument was validated in American and European trials, with people from Germany, France, England, Italy and Poland involved (Giuliano et al., 2008) although it has been used also in the Spanish community (Bar-Or, Salottolo, Orlando, Winkler, & Group, 2012; Buvat, Tesfaye, Rothman, Rivas, & Giuliano, 2009).

The Premature Ejaculation Diagnostic Tool (PEDT) will be used for the diagnosis. It takes five measurements in order to evaluate difficulty in delaying the ejaculation, ejaculation occurring before the patient wanted it, ejaculation with little stimulation, frustration related to premature ejaculation, and the couple's opinion about ejaculation. The test-retest reliability is 0.82 and all values statistically distinguish and differentiate statistically between PE and non-PE patients.

The Golombok-Rust Inventory of Sexual Satisfaction (GRISS) will also be applied. This is a brief 28-question questionnaire to assess the existence and severity of sexual problems in both members of a heterosexual relationship (Rust & Golombok, 1985, 1986). This questionnaire provides separate scores for men and women on 3 shared scales (avoidance, non-sensitivity, and dissatisfaction) and 6 gender-specific scales (impotence, premature ejaculation, anorgasmia, vaginismus, infrequency, and lack of communication) with acceptable values of reliability and validity (Rust & Golombok, 1985, 1986). The instrument was validated in the English community and is already being used in Spain in the official Master's degree in Sexology at the University of Almeria (García González, 2013; López Lorente, 2013).

The external masturbation aid will be the Myhixel I device manufactured by the company , NEW WELLNESS CONCEPT SL. (ANNEXED 2).

The Lubricant to be used in the trial will be Myhixel lube.

Waldinger, M. D., Zwinderman, A. H., Olivier, B., & Schweitzer, D. H. (2008). Geometric Mean IELT and Premature Ejaculation: Appropriate Statistics to Avoid Overestimation of Treatment Efficacy. *The Journal of Sexual Medicine*, 5(2), 492–499

Collaborator's signature:
Instituto Sexológico Murciano

INSTITUTO SEXOLOGICO MURCIANO
N.R.S 20300055
[contact]
www.isemu.es | [contact]

Lead Researcher's signature
[name]

Annexed 1

Data collection forms

REGISTER OF EJACULATION TIMES

[figure not shown]
[figure not shown]
[figure not shown]
[figure not shown]
[figure not shown]
[figure not shown]
[figure not shown]
[figure not shown]
[figure not shown]
[figure not shown]
[figure not shown]
[figure not shown]

[figure not shown]
WEEK:

NAME:

MONDAY TUESDAY WEDNESDAY THURSDAY FRIDAY SATURDAY SUNDAY

[figure not shown]
[figure not shown]

[figure not shown]

[figure not shown]
[figure not shown]
[figure not shown]
[figure not shown]
[figure not shown]
[figure not shown]

MASTURBATION

Record the time you take to ejaculate when masturbating

[figure not shown]
PENETRATION INTERCOURSE

Record the time you take to ejaculate after penetration

Annexed 2

ANEXO 2

[figure not shown]

PARTES.

1 – Pines magnéticos de carga

2 – Rosca hembra para aplique de manos libres.

- 3 – Rosca reguladora de succión.
- 4 - Botonera para control de vibración y calefacción.
- 5 – Conexión con resistencia calefactora
- 6 – Orificio de entrada de la manga
- 7 – Motor vibrador
- 8 – Bolsillo para albergar el motor vibrador.
- 9 – Palo calefactor.
- 10 y 11 – Sistema de imanes para asegurar el cierre.

**DIMENSIONES
PRINCIPALES**

MATERIALES Y PESO

PARTE	MATERIAL
MANGA	TPE (Elastómero termoplástico)
CUERPO	ABS
PALO CALEFACTOR	
RECUBRIMIENTO DEL CUERPO "SOFT TOUCH"	PDMS ("Silicona soft touch")

[figure not shown]
PARTE	PESO (gramos)
MANGA	340
MYHIXEL I (con manga)	670

MYHIXEL I (en uso, sin calefactor)	560
------------------------------------	-----

ELECTRONICA Y FUNCIONES

PARTE	MATERIAL
BATERÍA	POLÍMERO DE LITIO (650 Ma 3.7 V)
MOTOR VIBRADOR	~2 V (3.5 mm y 100 HZ)
CALEFACCIÓN	RESISTENCIA EN POLIAMIDA
CARGA	PINS MAGNÉTICOS + USB

1	2	3	4	5	6
LED 1+2	LED 1+2	LED 1+2	LED 1	LED 1	LED 2
CARGANDO	CARGADO	BATERÍA BAJA	CALENTANDO	TEMPERATURA ALCANZADA	VIBRACIÓN
Leds ON fijo	Leds OFF	Los leds parpadean alternativamente	Led ON Latente (ver link adjunto)	Led OFF	Led On Durante 10 sg y luego OFF

COLOR LEDS (1 y 2): **BLANCO CÁLIDO**

APPENDIX 3

SCT Exercise Program PATIENT FORMS

In the first week, we're going to start with what we call the **Stop and Go Flip Hole Program**.

OBJECTIVES

1. To become aware of the role of the pelvic floor in the orgasmic response.
2. To identify the pattern of muscle tension in the genital area that's necessary to ejaculate.
3. To identify the voluntary nature of that pattern of muscular tension that's necessary to ejaculate.

KEY POINTS

Perform the activity only after you've watched the video that corresponds to the activity Discovering the Pelvic Floor.

This activity is carried out individually.

Before carrying out the activity, the participant must understand its theoretical content.

It should be carried out a minimum of 4 times or until the participant is able to reach the objectives of this first week.

This activity isn't just about masturbation, but rather about becoming aware of the role of the pelvic floor.

STEPS TO FOLLOW

Find a quiet moment where you can't be interrupted. Turn off your phone, TV, and radio, and don't let children or other people living with you distract you.

Before you start, apply a few drops of lubricant to the Flip Zero device, which you will find in the kit. Start to caress your penis, slowly and progressively, until you get an erection. From this point you will start to masturbate using the Flip Zero device, paying attention to the changes that occur around the genital area and in the nearby muscles.

It's important that you try to identify how muscle tension increases in the genital area and muscles near it as your excitement increases. You must consciously identify these points of muscular tension or tightness in the legs, abdomen, buttocks and especially in the pelvic floor (under the testicles and in the anal sphincter).

Continue masturbating until you ejaculate and observe that in order to provoke the ejaculatory reflex, you don't only need to stimulate the penis, but you also need to create muscular tension in the area, and especially in the pelvic floor.

We can see, therefore, that muscular tension in the pelvic floor area is a necessary condition for ejaculation, and it is also a voluntary factor. This muscular group is the key to either delaying or accelerating the ejaculatory reflex.

If this muscle group, known as the pelvic floor, and especially the anal sphincter and the urethra, are not in tension, the ejaculation reflex cannot occur.

During the following three weeks we will continue with what is called the **Start-Stop Program**.

OBJECTIVES

1. To get to know the physiological changes in a complete male sexual response cycle.
2. To identify the changes in the musculature of the genital area in the pre-orgasmic phase.
3. To identify the voluntary nature of the muscular tension that initiates the pre-orgasmic phase.
4. To begin to exert control over this musculature involved in the pre-orgasmic phase.

KEY POINTS

Only perform this activity after having identified (in activity 1) the muscle tension in the genital area prior to ejaculation and having understood the role that the pelvic floor plays in the orgasmic response.

The activity is performed individually, trying to ensure that it lasts at least 5 minutes.

The participant must understand the theoretical content of the activity before performing it.

It will be performed as many times as necessary until the man is able to achieve the objectives of this second activity; we recommend a minimum of 4 times per week.

Again, this is not simply about masturbation, it's a self-control training activity.

STEPS TO FOLLOW

Find a quiet time and place where you won't be interrupted. Turn off your phone, TV or radio, and don't let children or other people living with you come near the bedroom.

Start to caress your penis, slowly and progressively, until you get an erection. You will then start masturbating with the lubricated Flip Zero device, paying attention to the changes in your genital area.

It's important that you try to identify how, as the excitement increases, the muscle tension in the genital area and muscles close to it increases. You must consciously identify these points of muscle tension or tightness in the legs, abdomen, buttocks and, especially, the pelvic floor.

Continue masturbating until you feel that you're about a minute or two away from ejaculation. At this point, stop stimulating yourself and try to identify how you have triggered the ejaculatory reflex, by generating muscle tension in the pelvic floor area and around the genitals.

Then, within a minute of stopping the stimulation, practice releasing the tension in that area, relaxing it, and paying special attention to the anal sphincter and urethra, which should become tension-free.

When you start stimulating yourself again, you should notice that, if you've really managed to release the tension, then you'll be moving away from a point of climax and that you're no longer so close to ejaculating. This process of stopping the stimulation and starting again should be done at least four times in each activity. Once you've done this at least four times, you will then allow yourself to proceed towards ejaculation, allowing the full muscle tension to occur in the genital area.

In the fifth week we're going to continue the process with what we call the **Stop and Go Program without interrupting stimulation.**

OBJECTIVES

1. To get to know the physiological changes of the complete male sexual response cycle.
2. To identify the physiological changes of the pre-orgasmic phase.
3. To identify the voluntary nature of the pre-orgasmic phase.
4. To strengthen the control of the pre-orgasmic phase using the pelvic floor muscles in conditions similar to intercourse.

KEY POINTS

The activity should only be carried out after the participant understands the role the pelvic floor plays in the orgasmic response, as well as having achieved the objectives of the previous weeks.

The activity is to be carried out individually.

Before carrying out the activity, the man must understand its theoretical content and watch the accompanying video.

It should be performed as many times as necessary until the man is able to reach the objectives of this third activity. We recommend a maximum of 5 times a week.

It isn't simply a question of masturbating, but, rather, of a guided self-control training activity.

STEPS TO FOLLOW

Find a quiet time and place where you won't be interrupted. Turn off your phone, TV or radio, and don't let children or other people living with you come near the bedroom.

Start to caress your penis, slowly and progressively, until you get an erection. You will then start masturbating with the well-lubricated Flip Zero device, paying attention to the changes in your genital area and surrounding areas.

It's important that you try to identify how, as the excitement increases, the muscle tension in the genital area and muscles close to it increases. You must consciously identify these points of muscle tension or tightness in the legs, abdomen, buttocks and, especially, the pelvic floor.

Continue masturbating until you feel you're a minute or two away from ejaculation if you continue as you are. At that point, while continuing to stimulate your penis with the masturbation device, and without changing the rhythm, focus your attention on the muscle tension in the pelvic floor area and around the genitals.

Then, and without any interruption in the stimulation, practice relaxing the area and releasing the tension, giving special attention to the anal sphincter and the urethra, which should be tension-free. To test whether this is the case, you can try to simulate urination, and this will relax the sphincters automatically.

If you have managed to release the tension, then you will notice then you'll be moving away from a point of climax and that you're no longer one or two minutes away from ejaculating. However, you need to ensure that you're constantly stimulating your genital area with the device.

This process of delaying the ejaculatory reflex should be performed at least four times in each masturbation activity. Once you've done this, you will finish the process letting the muscle tension process continue and ejaculating into the device.

In the seventh week, we'll continue the process with what we call the **Start-Stop Zero Program with small interruptions and the simulation of penetration through hip movements.**

OBJECTIVES

1. To get to know the physiological changes during the complete male sexual response cycle.
2. To identify the body's hip movements without the need to tense the pelvic floor area.
3. To identify the voluntary character of the aforementioned muscular tension during the pre-orgasmic phase.
4. To strengthen the control of the pre-orgasmic phase using the pelvic floor muscles in a similar way to intercourse and with hip movements.

KEY POINTS

The activity should only be performed once the participant has understood the role of the pelvic floor in the orgasmic response, as well as having successfully achieved the objectives of the previous weeks.

The activity should be performed individually and without the use of the hands to masturbate.

The participant should learn to move his hips without tensing the pelvic floor muscles.

The process should be carried out as many times as necessary until the man is able to reach the objectives of this seventh week; we recommend carrying out the process a maximum of 5 times in the week.

Again, this isn't simply a question of masturbating or reaching climax, but a guided training activity in muscle self-control.

STEPS TO FOLLOW

Find a quiet moment and place where you won't be interrupted. Use audiovisual material of a sexual nature to focus your attention and cause a higher level of excitement, as well as making you less sensitive to internal sensations.

You should then begin to caress the penis, slowly and progressively, until you get an erection. At that point, you should start to use the Flip Zero device, sufficiently lubricated, being aware of everything that's happening in your body at the same time. You should do this in a standing or kneeling position, using thrusting forward hip movements with the device in position, simulating penetration, and not using your hands.

Continue to perform these movements until you feel that you're a minute or two away from ejaculation, at which point, and without removing your penis from the masturbation device, focus on your muscle tension in the pelvic floor area and around the anal sphincter, with special attention to the buttocks. Next, practice releasing the tension in that area to leave it completely relaxed, giving special attention to the anal sphincter, buttocks, and pelvic floor muscles, which should be free of tension. In order to do this, you can try to simulate urination to relax these sphincters voluntarily.

If you've been able to release the tension successfully, then you'll notice that you're moving away from the point of climax and that you're no longer one or two minutes away from ejaculation. Remember that you must do all of this without removing your penis from the lubricated device. The key to controlling this tension is to move your hips as if you were hula-hooping, and, in this way, you can develop speed without causing muscle tension.

This process of delaying the ejaculatory reflex should be carried out as many times as necessary in each masturbation activity. The total duration of the exercise should be no less than 15 minutes, and, after this time, you can then allow the muscle tension to continue in the buttocks and anal sphincter and ejaculate into the device.

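### The only printed SCT exercise form has no arm label and is written for a Flip Zero device, not Myhixel I; its week-7 steps cannot be followed by group 1, which has no device

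*Protocol*

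**What the plan says.** Section 5.8 gives group 1 SCT alone and group 2 SCT with the device. It states that the exercise protocol is the same and the device is the only difference; section 9 repeats this. Sections 5.10 and 19 and Annex 2 identify the device as Myhixel I. Section 5.10 lists four exercises lasting 1, 3, 2 and 1 weeks and refers to Appendix 3 for their content. Its name for the last exercise combines constant stimulation with coital movements and mentions no device.

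Appendix 3 holds a single set of patient forms, with no group named:

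- Week 1 is titled "Stop and Go Flip Hole Program". It tells the man to "apply a few drops of lubricant to the Flip Zero device, which you will find in the kit", and then: "From this point you will start to masturbate using the Flip Zero device".
- Weeks 2 to 4: "You will then start masturbating with the lubricated Flip Zero device".
- Weeks 5 and 6: "You will then start masturbating with the well-lubricated Flip Zero device". Later the relaxation is practised "while continuing to stimulate your penis with the masturbation device".
- Week 7 is titled "Start-Stop Zero Program with small interruptions and the simulation of penetration through hip movements". Its key points include: "The activity should be performed individually and without the use of the hands to masturbate". Its steps call for Flip Zero, hip thrusting with the device in place, no hands, and ejaculation into the device.

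**The concern.** The second part of the main objective (5.7) is whether the device enhances SCT. That question needs two arms doing the same exercises, one with the device and one without. The only printed exercise content assumes a device throughout, and a man in group 1 cannot carry out its last exercise as written.

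Week 7 is the final training step and the one closest to intercourse, while the main parameter is intravaginal latency. If group 1 skips or improvises that week, a difference in IELT fold change mixes two things: having the device, and having done a penetration-like exercise. The analysis in section 14 cannot separate them.

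The product name is a lesser matter. A group 2 patient handed this form would read the name of a product that the protocol does not list as supplied. That is confusing, but by itself it does not alter the analysis.

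**Working it through.** This is a check of text; no power or sample-size figure is involved.

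**1. Device references in Appendix 3**, counted through the steps of each activity:

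| Activity | Device references | Of these, Flip Zero | Of these, Myhixel | Doable by hand once device words are dropped |
|---|---|---|---|---|
| Week 1 | 2 | 2 | 0 | yes |
| Weeks 2–4 | 1 | 1 | 0 | yes |
| Weeks 5–6 | 4 | 1 | 0 | yes |
| Week 7 | 5 | 1 | 0 | no |
| Total | 12 | 5 | 0 | 3 of 4 activities |

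The other 12 − 5 = 7 references are generic. Weeks 1 to 6 hold 2 + 1 + 4 = 7 of the 12. Removing those seven leaves instructions that work with manual stimulation.

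**2. Week 7 without a device.** Removing the five device references here leaves no source of stimulation, because the key points and the steps both exclude the hands. The affected share is 1 of 4 activities and 1 of 7 weeks.

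**3. For whom is the form meant?** Section 6 lists 30 Myhixel I devices and courier service for 30 kits, against 50 planned patients (5.11) and 24 needed per group (section 12). Thirty is enough for one arm (30 ≥ 24) but not for both (30 < 2 × 24 = 48). The week-1 form says the device is in the kit. The likely reading is therefore that this is the group 2 form, though nothing on it says so. On that reading, the protocol prints only exercise names and durations for group 1.

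**4. Week-7 content against 5.10.** The durations agree: 1 + 3 + 2 + 1 = 7 weeks, as in section 16. Coital movements in 5.10 correspond to the hip movements in the form. The two disagree on stimulation: constant in 5.10, with small interruptions in the form's title. The steps do not settle it. They keep the penis in the device during relaxation and advise a circling hip movement, but do not say whether thrusting continues or pauses.

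**5. Could the gap come from removed text?** The form runs without a break from week 1 to week 7, and the removed parts of the protocol come before it. Removal does not appear to explain the missing group 1 steps.

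**The case against.** The strongest reply is that the protocol is not the whole intervention. Section 5.7 places SCT in an Android app, and the forms refer to videos. Either could hold a device-free version of every exercise. This stands, and it limits the point: the protocol does not show that group 1 lacks instructions, only that the content cited in 5.10 does not supply them for week 7.

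A second reply is that the main text already gives group 1 its rule: do the same exercises without the device. That works for weeks 1 to 6. It fails for week 7, where the hands are also excluded.

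A third reply is that hands-free use belongs to the device, since Annex 2 lists a thread for a hands-free fitting. An effect of hands-free training would then be part of the device effect and not a confounder. This is a fair reading, but sections 5.8 and 9 do not state it. If it is intended, a sentence there would settle the matter.

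Some stronger readings are tempting but unsupported:

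- A reader might infer that the trial will use a different product. Sections 5.10, 6 and 19 and Annex 2 all name Myhixel I; the form looks like text carried over from another product, although the protocol does not say so.
- A reader might infer that both arms receive a device. The supply of 30 argues against it.
- A reader might see a contradiction in section 6 between 30 and 50 lubricant bottles. The 30 can be the company's contribution and the 50 the whole-project budget.
- A reader might say that none of the form titles matches 5.10. Most are near-synonyms; the substantive conflict is the one in week 7.

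**Conclusion.** The point holds in a limited form and should be fixed before first inclusion. The appendix cited for a program common to both arms prints one unlabelled form, names the wrong product in five places, and contains a final exercise that group 1 cannot perform. Its week-7 title also conflicts with 5.10 on whether stimulation is constant.

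The gap covers one activity of four and one week of seven. Its effect on IELT fold change cannot be quantified from the protocol, and no loss of power is claimed. The consequence for interpretation rests on one assumption: that the app and videos do not give group 1 its own week-7 steps. If they do, what remains is a correction of the printed form. If they do not, the comparison estimates the device together with a different or missing week-7 exercise, not the device as the only difference. It would go too far to infer that the comparison is invalid, since six of the seven weeks can be matched across arms with simple edits.

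**What to change.** Before the first patient is included:

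1. Label the printed form as the group 2 form. Replace Flip Zero with Myhixel I in its five places, and replace the Flip Hole and Start-Stop Zero titles with the names in 5.10.
2. Add a group 1 form with the same steps and no device text.
3. Have the investigator state what group 1 does in week 7, for example coital hip movements with manual stimulation. The group 1 form must then drop the hands-free requirement. Alternatively, state in 5.8 and 9 that week 7 is hands-free in group 2 only, and word the conclusion as the effect of the device including its hands-free exercise.
4. Make the week-7 steps, and not only the title, say whether stimulation continues or pauses during relaxation. A new title alone would leave this open. Then check that the app and videos agree with both forms.

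The cost is revising one form, writing a second and adding a few sentences, with no extra patients or visits. If week 7 stays different between arms, the conclusion becomes slightly narrower.
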